### 3. Interventions

In the study group, a portable TENS 7000 device (Roscoe Medical, Middleburg Heights, OH, USA) was used for stimulation. The device was calibrated for a frequency of 50 Hz and its intensity was modulated according to the patient's comfort (pulse amplitude of 1-4). Each session lasted 25 minutes. The self-adhesive electrodes were connected to the channels of the device and **attached to the patient's skin** of both facial sides next of the major salivary glands (parotid and submandibular glands), passing through the mandibular branch of the trigeminal

nerve as shown in figure 1. The patients were submitted to the respective treatment protocol once a week for eight consecutive weeks, totaling 8 treatment sessions.

In the control group, photobiomodulation was applied using a laser whose parameters are represented in table 1. During laser application, the patients and the clinician wore the protective glasses (figure 2).

#### 4. Outcomes

Pain/burning was the primary outcome and was measured on a visual analogue scale (VAS; 0-10 cm). The patients were asked to choose a number from 0 to 10 on the scale to describe the level of intensity of their symptoms.

Changes in unstimulated salivary flow, xerostomia, and dysgeusia were the secondary outcomes. Saliva was collected as described by Navazesh and Kumar [26] and patients with an unstimulated salivary flow rate  $< 0.1$  ml/min were classified as having hyposalivation.

Information on xerostomia was collected according to the method of Murray Thomson et al. (2006) using a standard question and the Xerostomia Inventory (XI). Patients answered the following question: "How often does your mouth feel dry?" (response options: "never", "occasionally", "frequently", "always"). On each occasion, those who gave either of the latter two responses were categorised as xerostomic. The XI was used to obtain information on the severity of xerostomia symptoms, being an 11-item summated rating scale which combines the responses to 11 individual items into a single continuous scale score which represents the severity of chronic xerostomia, and higher scores represent more severe symptoms. The patients were asked to choose one of five responses ("never", scoring 1; "hardly ever", 2; "occasionally", 3; "fairly often", 4 and "very often", 5) to the following statements referring to the previous 4 weeks: "my mouth feels dry"; "my lips feel dry"; "I get up at night to drink"; "my mouth feels dry when eating a meal"; "I sip liquids to aid in swallowing food"; "I suck sweets or cough lollies to relieve dry mouth"; "my throat feels dry"; "the skin of my face feels dry"; "my eyes feel dry"; "my lips feel dry" and "the inside of my nose feels dry". Each individual's responses were scored and summed to give a single XI score.

Dysgeusia was analyzed using an adaptation of the method proposed by Muller et al. [28], in which the four basic tastes at four different concentrations are tested. Urea was used as bitter taste as proposed by Henn et al. [29] (sucrose solution: 0.4 g/mL, 0.2 g/mL, 0.1 g/mL, 0.005 g/mL; sodium chloride: 0.25 g/mL, 0.1 g/mL, 0.04 g/mL, 0.016 g/mL; citric acid: 0.3 g/mL, 0.165 g/mL, 0.09 g/mL, 0.05 g/mL; urea: 0.005 g/mL, 0.04 g/mL, 0.02 g/mL, 0.01 g/mL). Filter paper strips were impregnated with the test solutions as proposed by Kettenmann et al.

[30]. The strips were placed in the center of the tongue and the patient was asked to identify the taste. The 10th percentile was used to define the presence or absence of dysgeusia.

The primary and secondary outcomes were collected at baseline (T0), after the 4th treatment session (T1), after the 8th treatment session (T2), and 30 days after the end of treatment (T3).

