## 8. Statistical analysis

All data were analyzed using the Statistical Package for the Social Sciences 25.0 (SPSS). First, the collected data were submitted to descriptive analysis. Fisher's exact test was then used to determine whether statistically significant differences in systemic alterations, psychiatric disorders and medication use exist at T0 between the TENS and PBM groups.

The quantitative data (VAS score and unstimulated salivary flow) were analyzed using the Kolmogorov-Smirnov normality test to assess if the data are normally distributed, which

was confirmed based on the mean error. Two-factor ANOVA was used to analyze intergroup (TENS and PBM) and intragroup (repeated measures at T0, T1, T2 and T3) differences in mean VAS scores and unstimulated salivary flow. For this purpose, the assumptions of sphericity were tested using the Mauchly test. The post-test of intergroup and intragroup interactions was carried out based on Bonferroni corrections, as well as using the trend test of the interaction between time and intervention. A level of statistical significance of 95% was adopted for all tests.

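### No adverse events or tolerability are collected for either device, and non-compliers leave the sample without reasons by arm, so the trial cannot support a statement on the relative tolerability of TENS and PBM

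*Combined protocol and SAP*

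**What the plan says.** Section 4 names the outcomes: "Pain/burning was the primary outcome and was measured on a visual analogue scale (VAS; 0-10 cm"), and "Changes in unstimulated salivary flow, xerostomia, and dysgeusia were the secondary outcomes". It sets the collection points: "The primary and secondary outcomes were collected at baseline (T0"), then "after the 4 th treatment session (T1), after the 8 th treatment session (T2"), and finally T3, 30 days post-treatment. Xerostomia is measured partly with an inventory that looks back four weeks. Hyposalivation (flow below 0.1 ml/min), xerostomic status and dysgeusia are each defined as a classification of the individual patient.

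Section 3 gives treatment "once a week for eight consecutive weeks, totaling 8 treatment sessions". TENS runs for 25 minutes through adhesive electrodes on the face, and "its intensity was modulated according to the patient's comfort (pulse amplitude of 1-4"). For PBM, "During laser application, the patients and the clinician wore the protective glasses".

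Section 2 excludes from the sample patients who did not comply with the treatment protocol. Section 8 starts with an unspecified descriptive step, uses Fisher's exact test for baseline characteristics at T0, and applies a two-factor ANOVA to "differences in mean VAS scores and unstimulated salivary flow". It names no analysis of harms, withdrawals or exclusions.

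**The concern.** The trial compares two active device treatments without blinding, so how patients tolerate each one bears on any choice between them. The protocol's own description shows that tolerability matters: TENS intensity is adjusted to comfort, and the laser calls for eye protection. Yet no outcome, form, time point or analysis is set aside for unwanted effects.

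The exclusion rule makes this worse. A patient who stops because a session was unpleasant can be classed as non-compliant and removed. The patients most informative about tolerability are then the ones most likely to be missing, and possibly more often in one arm than the other. Analysts cannot recover what was never recorded, so this is more than a gap in the description of the analysis. A later statement that TENS is safe, or better tolerated than PBM, would have no data behind it.

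**Working it through.** **Inputs.** Outcomes and collection points: section 4. Eight weekly sessions: section 3. Exclusion of non-compliers: section 2. Analyses: section 8. Total of 28 patients in two groups: section 5. The allocation ratio is not stated, so 14 per arm is an assumption.

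**Step 1: where each kind of event would appear under the plan.**

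| Event | Record under the plan |
|---|---|
| Skin reaction at an electrode or laser site | None. The nearest item is facial-skin dryness in the Xerostomia Inventory |
| Pain or discomfort during a session | None. The VAS rates the patient's symptoms at T0 to T3 |
| TENS amplitude actually used | Adjusted to comfort, but recording is not mentioned |
| Stopping because of discomfort | Patient may be excluded under section 2; no reasons by arm |
| Burning above the patient's own T0 value | VAS is held for each patient; no count planned |
| Flow newly below 0.1 ml/min | Flow is held for each patient; no count planned |
| New dysgeusia | Held for each patient as present or absent; no analysis named |

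The first four rows are data that would not exist, or would not be reported. The last three are data that exist but are not tabulated.

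**Step 2: sessions.** Outcomes are collected after sessions 4 and 8, so 8 − 2 = 6 sessions (1–3 and 5–7) have no scheduled outcome collection. That count is about efficacy measures and is not the defect. For adverse events the number of sessions with planned recording is 0 of 8, because sessions 4 and 8 do not include it either.

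**Step 3: what means show.** An invented example for one arm of 14: if 11 patients fall by 3 points and 3 rise by 2, the mean change is (11 × (−3) + 3 × 2)/14 = −27/14 = −1.93. The ANOVA shows an improvement of about 1.9 points, and the three worse patients appear only if someone counts them. This applies to VAS and flow, the only variables in the ANOVA.

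**Step 4: what complete recording could establish.** The plan gives no figure for harms to reproduce. Its total of 28 is taken as stated. (It does not follow from section 5's inputs as a two-group comparison: 2 × (1.645 + 0.842)²/0.70² = 25.2, so 26 per group and 52 in total. That is a separate matter, on which this point does not depend.)

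- Zero events in 14, one-sided 95% upper bound: 1 − 0.05^(1/14) = 19.3%. Upper limit of the two-sided exact interval: 1 − 0.025^(1/14) = 23.2%.
- Zero events in all 28: 1 − 0.05^(1/28) = 10.1% one-sided, and 1 − 0.025^(1/28) = 12.3% two-sided.
- Chance of at least one event in 14, 1 − (1 − p)^14, at assumed true risks of 1%, 5%, 10% and 20%: 13%, 51%, 77% and 96%.

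Only common harms could be ruled out in either arm. These figures describe the limits of 14 patients with full capture. They do not measure the damage done by not recording.

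**The case against.** The strongest reply is that the plan is not blind to deterioration. A reader might infer that the trial cannot show whether any patient became worse. The documents do not support that: every patient has VAS, flow, xerostomia and taste data at T0, T1, T2 and T3, so worsening can be counted at no cost in new data. A reader might also infer that comparing means hides new dysgeusia. It does not: the ANOVA covers only VAS and flow, and dysgeusia is a present/absent classification. The unspecified descriptive step might display such changes, though nothing says that it will.

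Nor should six sessions without outcome collection be read as six unobserved sessions. Nothing requires VAS or saliva every week, and with weekly sessions the inventory's four-week recall at T1 and T2 reaches back over the sessions in between, for dryness symptoms. Section 3 says that intensity followed comfort. It does not say that current was raised to the edge of discomfort, and it calls PBM the control without describing it as established.

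All of this stands, and it limits the point to adverse events, tolerability and unexplained exclusions. None of it supplies a place where a skin reaction, painful stimulation or a reason for stopping would be written down. A worsening table alone would not repair this: small VAS rises may be noise, and patients excluded under section 2 would be missing unless deliberately included.

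**Conclusion.** The concern holds in this form and should be acted on. The plan describes no collection or analysis of adverse events or tolerability for either device, and it drops non-compliers with no reporting of reasons by arm. A statement on the relative tolerability of TENS and PBM would therefore be unsupported. Worsening on the measured outcomes can be counted, but no count is planned. No effect on the efficacy comparison is claimed here.

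The size of the gap is none of eight sessions with planned recording of harms. Even with full recording, zero events in an arm would exclude only risks above about 19% (one-sided 95%). That figure assumes 14 per arm. The conclusion covers sections 1 to 8; a harms procedure set out in front matter or consent material, which was not available, would need to be checked.

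**What to change.** **If sessions remain, or for a repeat of the trial.** At each of the eight existing sessions and at T3, ask one fixed question on unwanted effects since the last contact, and record the answer and the TENS amplitude used. Report by arm, for everyone who received at least one session, the adverse events and the exclusions or discontinuations with reasons, with exact 95% intervals.

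**From data already held.** As a descriptive supplement, tabulate by arm at T1, T2 and T3 the patients with VAS above their own T0 value, flow newly below 0.1 ml/min, or new dysgeusia. Include whatever data exist for excluded patients, and note that small VAS rises may be measurement noise.

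**If sessions are complete,** as section 1's study period of April 2021 to February 2022 suggests, prospective recording is no longer possible. Report exclusions with known reasons by arm, state that harms were not systematically collected, and make no safety or tolerability claim. The supplementary table can still be added.

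**Cost.** Prospectively, a short form at visits that take place anyway. Retrospectively, one table, a list of exclusions and a sentence on limitations. The intervals for harms will be wide, and the report has to say so.

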## 5. Sample size

The sample size was calculated according to Sikora et al. [31] who compared the efficacy of PBM to a placebo group (laser off). In that study, the mean and standard deviation (SD) of the VAS score in the placebo group at the end of treatment was  $2.417 \pm 2.918$ . Considering that acceptable improvement in the PBM group would be at least 10% after the intervention, we obtained an effect value ( $E$ ) = 2.17. The sample size was then calculated using a t-test for comparing the means of continuous variables, whose standardized effect size was 0.70 assuming a one-sided alpha error of 0.05 and a beta error of 0.20, resulting in 28 patients divided into two intervention groups.

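### Dysgeusia is cut to present/absent at a 10th percentile whose reference is not stated, and Section 8 gives it no analysis, although the taste test could be analysed as a count

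*Combined protocol and SAP*

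**What the plan says.** Section 4 (Outcomes) lists dysgeusia among the secondary outcomes: "Changes in unstimulated salivary flow, xerostomia, and dysgeusia were the secondary outcomes". Primary and secondary outcomes are recorded at T0, T1, T2 and T3. The taste test adapts a cited method, "in which the four basic tastes at four different concentrations are tested", with urea as the bitter stimulus taken from a second source. No scoring rule is given. The section then states: "The 10th percentile was used to define the presence or absence of dysgeusia".

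Section 8 (Statistical analysis) opens its account of the continuous outcomes with "The quantitative data (VAS score and unstimulated salivary flow) were analyzed", and its two-factor repeated-measures ANOVA covers those two variables only. Fisher's exact test is assigned to baseline comparisons of systemic alterations, psychiatric disorders and medication use. Dysgeusia appears under neither.

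**The concern.** A percentile has no meaning until one says of what. Here it could be a percentile of published norms, of the trial sample at T0, of the trial sample at each visit, or of a score for each taste separately. Two analysts working from the same strips could report different dysgeusia outcomes, and Section 8 would not tell either of them how to compare the arms.

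The label also throws information away. A patient who moves from 5 to 9 correct answers counts as changed only if the cut lies between those values. With 28 patients the trial has little information to spare, and change in dysgeusia is one of only three secondary outcomes. The likely consequence is a report of no taste difference that says more about the label than about the treatments.

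**Working it through.** **The plan's own figure.** None is given for dysgeusia. The only design figure is for VAS in Section 5: "whose standardized effect size was 0.70", one-sided 5%, 80% power, "resulting in 28 patients divided into two intervention groups". The two-sample formula 2[(1.645 + 0.842)/0.70]² gives 25.2, so 26 per arm or 52 in total. The stated 28 is not reproduced. That is a separate matter; here 28 is taken as it stands.

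**Inputs.**
- From the documents: 28 patients, two arms, four tastes, four concentrations, four visits.
- By inference: 14 per arm (equal allocation); 4 × 4 = 16 items, hence a 0-16 count.
- Assumed: a normal score; a shift in one arm of 0.7 SD (the VAS effect size, borrowed) or 1.0 SD; 10-80% of the unshifted arm below the cut; two-sided 5% (Section 8 does not state sidedness); Fisher's test for the label (no test is named).

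**Information kept by the label.** For a normal score cut at quantile p, the relative efficiency is φ(z_p)²/[p(1−p)]. At p = 0.10, z = −1.2816 and φ = 0.1755, so 0.1755²/0.09 = 0.342.

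| Below the cut | Kept | Lost |
|---|---|---|
| 10% | 34% | 66% |
| 20% | 49% | 51% |
| 30% or 70% | 58% | 42% |
| 40% or 60% | 62% | 38% |
| 50% | 64% | 36% |

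**Power of the score at 14 per arm.** Noncentral t, 26 df, noncentrality d√(14/2): 1.85 for d = 0.7 and 2.65 for d = 1.0. Power is 43% and 72%.

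**Power of the label at 14 per arm.** With p below the cut in one arm, the shifted arm has Φ(Φ⁻¹(p) − d). Exact enumeration of Fisher's test gives:

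| p | Shifted arm, 0.7 SD | Power | Shifted arm, 1.0 SD | Power |
|---|---|---|---|---|
| 10% | 2.4% | 0.7% | 1.1% | 0.8% |
| 20% | 6.2% | 5.8% | 3.3% | 8.5% |
| 30% | 11.0% | 12% | 6.4% | 21% |
| 40% | 17.0% | 16% | 10.5% | 30% |
| 50% | 24.2% | 18% | 15.9% | 36% |
| 60% | 32.8% | 17% | 22.8% | 37% |
| 70% | 43.0% | 17% | 31.7% | 36% |
| 80% | 55.6% | 18% | 43.7% | 37% |

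Part of the gap is Fisher's conservatism. At p = 50% a normal approximation gives 28% (0.7 SD) and 48% (1.0 SD), still below 43% and 72%.

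**If the percentile were re-derived from trial data at each visit.** 10% of 28 is 2.8, so about 3 patients would be labelled every time. The most extreme split, 3 v 0, gives two-sided p = 2 × C(14,3)/C(28,3) = 2 × 364/3276 = 0.22. Ties on a 0-16 count blur this: in simulation the labelled share averaged about 8% (strictly below the cut) or 14% (at or below). Even 4 v 0 gives p = 0.098.

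**The case against.** The strongest reply is that silence is not a defect. The text says "Dysgeusia was analyzed using an adaptation of the method proposed by" a cited source, and the reference for the percentile may lie there. That is fair: the reference is not stated, which is different from there being none. It does not remove the gap, because the test is an adaptation with a substituted bitter stimulus, and the plan does not say that any norm carries over.

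A reader might infer that the rule pins the dysgeusia rate near 10% and so cannot show change. That needs a cut recomputed from trial data at every visit, which the text neither says nor excludes. With an external norm, or a cut set once at T0, later rates can move.

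A reader might also infer that the trial is nearly certain to miss a real taste effect, with power under 1%. That holds only if about 10% of patients fall below the cut. With 40-80% below it, the label has 16-18% power at 0.7 SD and 30-37% at 1.0 SD. Nor is most of the information lost at every cut: with 30-70% below it, the loss is 36-42%.

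Two further points stand. The 0-16 sum, its normality and Fisher's test are assumptions; a percentile for each taste would also fit the text. And the score itself misses a 0.7 SD effect 57% of the time, so the small sample remains the main limit.

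**Conclusion.** The concern holds in a limited form. The cut-off is not reproducible from the plan, dysgeusia has no stated analysis, and reducing the taste test to a label loses information that a count would keep. Under the assumptions above, the score has more power than the label at every cut tried. The size of the advantage cannot be fixed from the documents, because it depends on the share of patients below the cut, the true effect and the test chosen. A fixed 10% rate is a possibility to be ruled out in writing, not something the plan states. For a secondary outcome this is a worthwhile, inexpensive improvement and does not threaten the primary analysis.

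**What to change.** Define the dysgeusia outcome as the number of correctly identified taste strips, and write down the scoring rule. Compare TENS and PBM at T2 by ANCOVA adjusted for the T0 score. If consistency with VAS and salivary flow is preferred, use the Section 8 repeated-measures model instead. Choose one: that model spans T0-T3 and has no baseline adjustment at T2.

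Keep the present/absent label as a descriptive summary. State its reference population, the score it applies to and the cut-off in strips. Hold that one cut-off fixed from T0 to T3 and never re-derive it at each visit.

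The cost is a few sentences in Sections 4 and 8 and a re-analysis, provided the individual strip answers were kept. The count is less familiar to clinicians than a prevalence, which can still be reported beside it. Section 1 describes a trial run from April 2021 to February 2022, and the plan is written in the past tense, so the change of outcome should be labelled as post hoc.

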### 2. Participants

Patients older than 18 years who had a burning or dysesthetic sensation in the oral mucosa that recurred daily for more than 2 hours per day for more than 3 months, in the absence of clinically evident causal lesions [4], were included in the study. We also included patients with hyposalivation or any systemic alteration that could be related to a burning sensation in the oral mucosa but who did not have clinical alterations in the oral mucosa such as erosive lichen planus, geographic tongue, infections, allergic reactions, trauma, or injuries caused by physical or chemical agents. Patients who did not comply with the treatment protocol of the study were excluded from the sample.

Before the beginning of treatment, clinical and sociodemographic data of the patients were collected and blood tests were requested (complete blood count, fasting blood glucose, total cholesterol and fractions, triglycerides, ferritin, vitamin B12, folic acid, zinc, thyroxine, triiodothyronine, and antinuclear antibodies).

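### T1 and T2 are tied to sessions received and T3 to an undefined end of treatment, so patients who stop early have no complete outcome schedule

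*Combined protocol and SAP*

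**What the plan says.** All references are to the combined protocol and SAP.

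- **Section 4 (Outcomes)** places the first follow-up assessment "after the 4 th treatment session (T1") and the next two "after the 8 th treatment session (T2), and 30 days after the end of treatment (T3"). It gives no day count from randomisation or first session, and no visit window. The end of treatment is not defined as either the patient's own last session or the planned end of the course.
- **Section 3 (Interventions)** gives the course as "once a week for eight consecutive weeks, totaling 8 treatment sessions". This stands in the TENS paragraph. Its wording points to each group's own protocol, which suggests that it covers both arms.
- **Section 2 (Participants)** states: "Patients who did not comply with the treatment protocol of the study were excluded from the sample". Non-compliance is not defined.
- **Section 8 (Statistical analysis)** uses a two-factor ANOVA for differences between groups and for "intragroup (repeated measures at T0, T1, T2 and T3) differences in mean VAS scores and unstimulated salivary flow". It names no method for missing visits.
- **Section 5 (Sample size)** ends with a calculation "resulting in 28 patients divided into two intervention groups", and **section 7 (Blinding)** says that blinding was not possible because the devices differ.

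No section provides for outcome collection in a patient who stops or falls behind.

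**The concern.** For a patient who keeps every weekly appointment, counting sessions and counting days give the same visits. They separate once a patient stops or slips. Whether and when the primary VAS outcome is measured then depends on something that happens after randomisation. In an open comparison of two very different devices, that could differ by arm.

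The stake is mainly missing data. The plan does not ask for a T2 value from someone who never reaches session 8, and values not collected at the time cannot be recovered later. A second, smaller issue concerns patients who complete the course late. If they are not treated as non-compliant, they are analysed under the same visit labels as patients measured earlier, and the plan sets no limit on the delay.

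**Working it through.** **Inputs.** Eight weekly sessions (section 3); T1 after session 4, T2 after session 8, T3 30 days after the end of treatment (section 4); 28 patients (section 5). Assumption: the weekly timetable applies to both arms. The laser parameter table was not available for this check. Days are counted from the first session, because the gap between randomisation and first session is not stated.

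**Full course.** One session a week for 8 weeks gives 1 × 8 = 8 sessions, which matches the plan. Session k falls on day 7 × (k − 1), so:

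- T1 = 7 × 3 = day 21
- T2 = 7 × 7 = day 49
- T3 = 49 + 30 = day 79

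**Early stopping after session k.** T1 exists only if k ≥ 4, and T2 only if k = 8. T3 depends on the reading:

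- Own last session: T3 = 7 × (k − 1) + 30, which is 8 − k weeks before day 79.
- Planned end of course: T3 = 49 + 30 = day 79 for everyone, a shift of 0.

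| Last session | T1 | T2 | T3, own last session | Weeks early | T3, planned end |
|---|---|---|---|---|---|
| 1 | none | none | day 30 | 7 | day 79 |
| 2 | none | none | day 37 | 6 | day 79 |
| 3 | none | none | day 44 | 5 | day 79 |
| 4 | day 21 | none | day 51 | 4 | day 79 |
| 5 | day 21 | none | day 58 | 3 | day 79 |
| 6 | day 21 | none | day 65 | 2 | day 79 |
| 7 | day 21 | none | day 72 | 1 | day 79 |
| 8 | day 21 | day 49 | day 79 | 0 | day 79 |

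The T1 and T2 columns do not depend on how the end of treatment is read; the T3 columns do. A patient who receives no session has no T1 or T2, and on the own-last-session reading no T3 either.

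**Delayed completion.** Each week lost before session 4 and made up later moves all three visits by 7 days. One such week gives T1 = 21 + 7 = day 28, T2 = 49 + 7 = day 56 and, because the last session is also a week later, T3 = 79 + 7 = day 86 if counted from that session.

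**What reaches the analysis.** Two steps stand between an early stopper's T3 and the treatment comparison:

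1. Section 2 removes non-compliers. On a plain reading, stopping at any k from 1 to 7 is non-compliance.
2. Every early stopper lacks T2. A repeated-measures ANOVA in its usual form keeps only patients with all four visits, so an early stopper's T3 would be dropped even if the patient were retained. This is the conventional behaviour of the method; the plan does not state it.

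**Weight of one patient.** 1/28 = 3.6% of the planned sample.

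**The case against.** The strongest reply has four parts.

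*The early T3 is only one reading.* Section 3 describes treatment as the eight-session course, and section 4 names T3 directly after the session-8 visit. The end of treatment can naturally mean the end of that course. This stands: a reader might infer that early stoppers do have a T3 up to 7 weeks early, but the documents do not say so. The 7 weeks is the maximum on one reading of an undefined term.

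*Mistimed values would mostly not be analysed.* A reader might also infer that the TENS versus PBM contrast at T3 mixes patients measured weeks apart because of early stoppers. Section 2 and the conventional ANOVA block that route for VAS and salivary flow, so this part also stands. Two things remain. Delayed completers have all four visits and can enter at unequal times, because section 2 does not say whether a missed or late session is non-compliance. And removing early stoppers is itself a loss of randomised patients.

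*The real issue is the exclusion in section 2.* It is the larger one, but lifting it would not be enough. With section 4 unchanged, a retained early stopper would still have no T2 and possibly no T1. Equally, changing section 4 alone would collect data that section 2 then discards. The two have to change together.

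*Measuring after a fixed number of sessions is a coherent choice for a fixed weekly course.* That is fair for patients on schedule, for whom nothing differs. It leaves no rule for the others.

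**Conclusion.** The point holds in a limited form. T1 and T2 follow sessions received, T3 follows an undefined end of treatment, and nothing is anchored to calendar time. By the plan's own definitions, stopping after sessions 1-3 loses T1 and T2, and stopping after sessions 4-7 loses T2. A delayed completer who is not excluded is measured later than the rest.

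The T3 shift is conditional: 1 to 7 weeks before day 79 if T3 runs from the patient's own last session, 0 if it runs from the planned end, both assuming weekly sessions in the two arms. As the plan is written, the main harm is outcome data lost after randomisation, possibly unequally between two unblinded devices. It is not a comparison contaminated by early T3 values.

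Each patient affected is about 3.6% of 28. The documents give no dropout or delay rate and no evidence on which patients would stop, so neither the size nor the direction of any bias can be stated.

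**What to change.** 1. **Section 4.** Set T1, T2 and T3 at the times the full schedule implies from the first session: about days 21, 49 and 79, each with a fixed window (for example ±3 days). For a randomised patient who has no session, count from the scheduled first session. Collect VAS, salivary flow, xerostomia and taste then for every randomised patient, whether or not the sessions were delivered.
2. **Record** the number of sessions received and the actual date of each assessment.
3. **Section 2.** Amend the exclusion so that patients who stop or fall behind stay in the analysis. Without this, step 1 does not affect the results.
4. **Section 8.** Use a method that accepts incomplete visits, such as a mixed model for repeated measures, in place of one that needs all four.

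**Cost.** A few sentences in three sections, with no added procedures or visits for patients on schedule. Patients with delayed sessions will have had fewer than 4 or 8 sessions at T1 or T2, so those visits will no longer describe the effect of a fixed number of sessions for them. Early stoppers must be asked back for visits already planned. The treatment schedule and decisions to stop are unchanged.

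**If collection is finished** (the document is written in the past tense), missing values cannot be recovered. The sponsor can still report actual visit days and sessions received by arm, and state how the end of treatment was applied.
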